### **1.3.3 TRANSPLANT SPECIFIC GUIDELINES CONTRADICT GUIDELINES FOR THE GENERAL PUBLIC**

Published transplant specific guidelines recommend longitudinal screening for asymptomatic wait-listed patients and contradict recommendations for the non-ESRD population (Table C, Appendix). The most recent American College of Cardiology / American Heart Association Guidelines on Peri-operative Cardiovascular Evaluation and Care for Noncardiac Surgery suggest evaluation of symptomatic patients, but do not encourage further testing for asymptomatic patients or those with a functional capacity of  $\geq 4$  METS (i.e. ability to climb a flight of stairs) irrespective of diabetic status, history of CAD, or presence of cardiac risk factors.(9)

### **1.3.4 NO-REGULAR USE OF SCREENING TESTS MAY BE SAFE IN WAIT-LISTED PATIENTS**

In our observational study of n=604 wait-listed patients in British Columbia, clinicians utilized screening tests for CAD based on ongoing clinical evaluation during wait-listing. This strategy resulted in fewer screening tests than recommended by guidelines (n = 171 versus 530 tests), and a trend toward a lower frequency of cardiovascular events (cardiovascular event rate in patients with and without the recommended frequency of investigation was 9.9 [95% CI, 7.1 to 13.7] and 6.7 [95% CI, 5.2 to 8.7] per 100 patient-years).(20) Two other observational studies also suggest that no-regular screening may be safe: In a single centre study of 514 wait-listed candidates who were screened based on clinical criteria, the incidence of cardiac events at 5 years in the 224 patient who were not screened was 5.3% compared to 19.7% among the 290 patients who were screened. The use of screening tests in this study was based on clinical judgment of the treating physician, and some of the tests were likely performed in patients who had symptoms suggestive of CAD. (43) Similarly, in another study of 600 wait-listed patients, 174 patients were considered high risk based on clinical criteria and underwent screening for CAD and only 5 (2.9%) were revascularized. Cardiac events were higher in screened patients 12/174 (6.9%) versus unscreened patients 19/426 (4.5%).(44)

### **1.3.5 SUMMARY WHY THE CARDIAC SCREENING TRIAL IS NEEDED**

Medical advances have led to a paradigm shift away from revascularization of clinically silent coronary stenoses in non-ESRD patients. Current evidence based recommendations for CAD management in non-ESRD patients contradict the opinion-based recommendations for wait-listed kidney transplant candidates. However, non-ESRD guidelines emphasize the importance of symptoms and assume a short time course between evaluation and surgery, and may be less relevant for wait-listed ESRD transplant candidates in whom the timing of future transplant surgery cannot be precisely determined. Further, the goals of screening in transplant candidates extend beyond ensuring peri-operative safety and include maintenance of eligibility for transplantation, and ensuring that the potential long-term health benefits of transplantation are realized.

Canadian transplant physicians uniformly screen patients prior to accepting them onto the waiting list and are unwilling to randomize patients to use or non-use of screening at this stage. However, the main health services impact of screening occurs during the years of wait-listing for transplantation and there is clinical equipoise to conduct a definitive trial to determine the utility of screening for CAD after activation the waiting-list. Further if no-regular screening is shown to be non-inferior, the clinical need for future studies comparing surgical versus medical management of coronary disease in asymptomatic transplant candidates will be significantly decreased.

## **2.0 PLAN OF INVESTIGATION**

### **2.1 Trial Objectives**

This pilot trial will determine the feasibility of a multi-center, randomized, parallel group definitive trial.(45) Asymptomatic wait-listed patients will be randomized to routine screening for CAD (i.e. Myocardial Perfusion Scintigraphy (MPS) or Dobutamine Stress Echo (DSE)) as per the current standard of care (Table 1) versus no regular screening during wait-listing. Patients enrolled in the pilot will be included in the definitive trial analysis. The pilot trial will include six Canadian transplant centres. The definitive trial will be conducted in over 20 centers in Canada Australia and New Zealand.

**2.1.1 PRIMARY OUTCOMES:** In line with our primary objectives, the primary outcomes are 1) protocol adherence; 2) enrolment rates and 3) consent rates. A patient will be considered adherent if they were adherent to their allocated screening strategy (regular versus no-regular screening) over the 24 month treatment period. Enrolment rates will be assessed monthly during the six month enrolment period. Consent rates will be defined as the proportion of patients enrolled among eligible patients approached for enrolment and will be defined after completion of the six month enrolment period.

**2.1.2 SECONDARY OUTCOMES:** In this pilot study the secondary clinical outcome is a composite outcome of cardiac death and non-fatal myocardial infarction (i.e. the proposed primary outcome in the definitive trial) and will be adjudicated by a blinded clinical endpoints committee using criteria from the POISE Trial.(46, 47). Total mortality, cardiovascular mortality, non-fatal cardiac arrest, stroke, life-threatening bleeding and major bleeding (ie. the proposed secondary outcomes in the definitive trial) will also be defined and adjudicated as in the POISE Trial.(46, 47).

**2.1.3 TERTIARY OUTCOMES:** Transplant events, wait-list holds and wait-list removals including the indication will be measured. We will also ascertain health care encounters related to the diagnosis and management of CAD. This information is required to: i) determine cost, and cost effectiveness of the two screening strategies in the proposed definitive trial; ii) document concurrent management practices that may impact the incidence of outcomes in the definitive trial. The information captured will include outpatient, day care, and emergency room use (including any diagnostic testing and all medical and surgical interventions (i.e. use of thrombolytics, revascularization procedures), inpatient encounters and resource utilization (hospitalizations, CAD-related procedural costs), physician consultations. Quality of life will also be measured using the EQ-5D.

## **2.2 Sample Size**

Adherence to screening strategies is of utmost importance to demonstrate separation between the two strategies and fidelity of our interventions. In the pilot trial, a sample size of 144 will produce a 95% confidence interval equal to the sample adherence prevalence plus or minus 5% when the true prevalence of adherent patients is hypothesized to be 90%. Thus, 72 patients will be allocated to each treatment group.

In the definitive trial, randomization of 2500 patients is required to demonstrate that no-regular screening is non-inferior to regular screening, with an absolute increase in the primary outcome of cardiac death and non-fatal MI  $\leq 1\%$  in the no-regular screening arm considered non-inferior.

## **3.0 ELIGIBILITY CRITERIA**

Inclusion of incident wait-listed patients (i.e. patients activated to the waiting list after the start of the trial) and prevalent wait-list patients (i.e. patients already on the waiting list before the start of the trial) will enable successful enrolment, and ensure a high proportion of patients undergo transplantation during study follow-up. Only patients with an anticipated transplant date  $> 12$  months from the date of enrolment will be included. The time to transplantation of wait-list candidates can be estimated in each center based on ABO blood type, and immunology testing for anti-HLA antibodies. Enrolment in the pilot trial will be enriched to include at least 66% prevalent wait-listed patients so that

approximately 50% of patients are expected to undergo transplantation during the 24 month pilot trial follow up period.

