**Inclusion Criteria:**  
At least 18 years of Age  
No symptoms of active cardiac disease  
Actively Wait-listed For Kidney Only Transplant  
No previous extra-renal transplant  
Anticipated date of transplantation > 12 months from date of enrollment  
Anticipated to require cardiac screening before transplantation\*

Duration of Screening 24 months or until date of transplantation

Duration of Follow Up  
27 months if not transplanted  
3 months post transplantation if transplanted within 24 months of enrollment  
27 months if transplanted more than 24 months after enrollment

\* Each site will determine the estimated time to transplantation based on PRA and ABO blood type. The site investigator will complete Table 3 which will be used to estimate a potential participants time to transplantation. Patients who require a routine cardiac screening test (see Figure 1) to determine regular screening schedule for patients (based on cardiac history) before the estimated date of transplantation, are eligible for study participation.

Title	A randomized trial of screening for coronary artery disease in kidney transplant candidates: Pilot Study
Project Office	SPH
Study Size	144
Study Design	Multi-center, open label, randomized controlled trial of regular screening versus no-regular screening for coronary artery disease in kidney transplant candidates
Primary objective	To determine the feasibility of a definitive trial. Feasibility is determined by 1) protocol adherence 2) enrolment rates 3) consent rates. A patient will be considered adherent if they were adherent to their allocated screening strategy (regular versus no regular screening) over the 24 month treatment period. Enrolment rates will be assessed monthly during the six month enrolment period. Consent rates will be defined as the proportion of patients enrolled among eligible patients approached for enrolment and will be defined after completion of the six month enrolment period.
Secondary Objective	To record the composite outcome of cardiac death and non-fatal myocardial infarction (i.e. the proposed primary outcome in the definitive trial). These outcomes will be adjudicated by a blinded clinical endpoints committee using criteria from the POISE Trial
Tertiary Objective	To record transplant events, wait-list holds, and wait-list removals including the indication. To ascertain health care encounters related to the diagnosis and management of CAD.

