### 1.1 Principal Research Question

For our definitive trial, we will determine if a strategy of non-use of regular screening tests (i.e. Myocardial Perfusion Scintigraphy or Dobutamine Stress Echo) is non-inferior with respect to the composite endpoint of non-fatal MI and cardiac death compared to screening all asymptomatic wait-listed patients at regular intervals as described in transplant specific guidelines published by the National Kidney Foundation (see Table 1 below ).(7)

Table 1. Frequency of screening for CAD in patients randomized to regular screening group	
Patient characteristics	Frequency of Screening
Diabetic patients	Every 12 months
Patients with prior coronary artery disease on coronary angiogram: If not revascularized If prior percutaneous intervention (angioplasty or stent) If prior coronary artery by-pass grafting (CABG)	Every 12 months Every 12 months 3 years after revascularization and then every 12 months
If prior CABG but incomplete revascularization	Every 12 months
If high risk non-diabetic: More than 20% per 10 years cardiovascular event rate risk according to Framingham or known CAD (clinical, EKG, or other evidence of CAD but without angiographically visualized coronary stenosis), or PVD, or ejection fraction $\leq 40\%$	Every 24 months
Non-diabetic low risk (includes all patients not included in the above categories)	Every 36 months

<https://www.cvdriskchecksecure.com/FraminghamRiskScore.aspx>

**Before proceeding with a large multi-centre trial, feasibility will be assessed in a 33 month pilot trial.** In the pilot trial, feasibility is the primary outcome and will be assessed by protocol adherence, patient enrolment and consent rates.

1) Protocol Adherence: A patient will be considered adherent if the observed number of screening tests performed equals the expected number of screening tests during the two year follow-up period (i.e. the expected number of tests in a diabetic patient who remains asymptomatic would be zero in the no-regular screening group, while the same patient would be expected to complete two screening tests during the 24 month treatment period in the pilot trial if randomized to regular screening). Our proposed sample size of 144 patients will produce a 95% confidence interval equal to the sample adherence prevalence plus or minus 5% when the true prevalence of adherent patients is hypothesized to be 90%.

2) Enrolment of 24 patients per month during the six month enrolment period.

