## **5.0 TRIAL MANAGEMENT OF PATIENT RANDOMIZED TO REGULAR AND NO-REGULAR SCREENING**

**5.1 Screening test schedule:** Patients randomized to regular screening will undergo non-invasive testing for CAD according the 2005 National Kidney Foundation Guidelines (Table 1 above).(7) Patients randomized to no-regular screening will not undergo regular non-invasive testing for CAD in the absence of symptoms. Patients in both groups who develop symptoms of angina or an angina equivalent, will be investigated according to the local standard of care which may include the use of non-invasive or invasive cardiac testing. Patients will remain on the pilot trial protocol (i.e. regular or no-regular screening) until death, non-fatal MI, transplantation, permanent removal from the waiting list for any reason, or 24 months after enrolment in the pilot trial.

**5.2 Type of non-invasive cardiac screening test:** The choice of non-invasive test(s) will be according to the existing practice of each transplant center. The National Kidney Foundation guidelines recommend that testing should be done with an exercise or pharmacological stress echocardiographic or nuclear imaging test.(7) The choice of exercise or pharmacological stress is determined by the presence of physical limitations (e.g. osteoarthritis) in transplant candidates. The high prevalence of left ventricular hypertrophy in ESRD patients may also decrease the utility of ECG treadmill testing.(6) The type of test used will be documented in all instances.

**5.3 Investigation and management of an abnormal screening test:** The management of an abnormal screening test including performance of coronary angiography as well as treatment of coronary stenoses will be carried out as per the usual standard of care in individual transplant centers and will not be influenced by the investigators or study personnel in any way. CAD-related medical and surgical interventions will be recorded in both groups.

**5.4 Management of patients who develop clinical symptoms of CAD:** Any patient developing clinical symptoms of CAD (e.g. angina, congestive heart failure, or new arrhythmias) will be evaluated according to the standard of care in individual transplant centers and may include the use of non-invasive cardiac stress testing. Management of symptomatic CAD including revascularization will be according to the standard of care at

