## **6.0 FOLLOW-UP**

During wait-listing, follow-up telephone interviews and chart reviews will be performed every six months, with a final follow up interview at 27 months after enrolment performed in patients who do not undergo transplantation within 24 months of the date of study enrolment.

Patients who undergo transplantation during the first 24 months after enrolment will be followed until three months after the date of transplantation. A chart review will occur at the time of discharge from hospital, and an in person or telephone interview and chart review will be performed 3 months after transplantation.

For the small number of patients who undergo transplantation  $\geq$  24 months after enrolment, the last follow up will be 27 months after the date of enrolment even if the 3 months of post transplant follow up are not possible. A chart review will occur at the time of discharge from hospital, and an in person or telephone interview and chart review will be performed 27 months after enrolment.

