## **7.0 TRIAL OUTCOME ASCERTAINMENT**

Standardized Case Report Forms will be used to assess all outcomes and study personnel will undergo formal orientation to these CRFs.

**Primary outcomes:** 1) Protocol adherence: We will define adherence by completion of the expected number of screening tests during follow up. For example, the expected number of screening tests in a diabetic patient who did not develop symptoms would be zero in the no-regular screening group, while the same patient would be expected to completed two annual screening tests if randomized to regular screening. Tests performed for clinical symptoms of CAD will be excluded from the determination of adherence.

Screening tests in patients randomized to the regular screening arm will be arranged by study personnel under direction of the site investigator. The study personnel will advise participants of their screening test and follow up directly with the testing facility to determine completion of the test and obtain test results. Use of cardiac screening tests and the reasons for testing, in both treatment groups will be determined using the following procedure: Patients will be interviewed in person during regular dialysis treatments or via telephone every six months. If an unscheduled test was performed the patient will be asked about the reason for test (i.e. presence of symptoms) and the identity of the organizing physician. We believe telephone interviews are feasible in this relatively healthy cohort of wait-listed patients. Patient interviews will be supplemented by review of the transplant center and dialysis patient chart or with treating physicians as necessary every six months. 2) Enrolment will be determined monthly from the Ottawa Hospital Research Institute (OHRI) which issues the randomization scheme.

3) Consent rate: Each transplant center maintains an up-to-date record of incident and prevalent active wait-listed patients. Eligibility criteria will be abstracted from the transplant center chart to a standardized case report form. The case report form will be completed by the study co-ordinator and will include the estimated time to transplantation as determined by the site investigator.

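### Does the adherence outcome mis-score the half of participants expected to be transplanted before 24 months?

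*Combined protocol and SAP*

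**What the plan says.** Section 3.0 enriches enrolment for prevalent wait-list patients so that "approximately 50% of patients are expected to undergo transplantation during the 24 month pilot trial follow up period", and section 4.0 repeats the 50% as an aim. Section 5.1 keeps patients on their assigned protocol "until death, non-fatal MI, transplantation, permanent removal from the waiting list for any reason, or 24 months after enrolment in the pilot trial". The synopsis puts it as "Duration of Screening 24 months or until date of transplantation".

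Adherence is described in three places:

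- Section 1.1: a patient is adherent if the number of tests performed "equals the expected number of screening tests during the two year follow-up period". Its example is a diabetic patient without symptoms: none in the no-regular arm, while in the regular arm "the same patient would be expected to complete two screening tests during the 24 month treatment period".
- Section 2.1.1: a patient counts if "adherent to their allocated screening strategy (regular versus no-regular screening) over the 24 month treatment period".
- Section 7.0: "We will define adherence by completion of the expected number of screening tests during follow up". Tests prompted by symptoms are left out of the count.

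Section 6.0 sets the follow-up: "Patients who undergo transplantation during the first 24 months after enrolment will be followed until three months after the date of transplantation". Section 9.0 plans descriptive summaries of feasibility and adds no scoring rule.

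**The concern.** If half of participants are transplanted within 24 months, about 72 of 144 (36 per arm) leave the screening protocol early. A count that still expects 24 months of tests from them marks some as non-adherent although nothing due was missed.

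The error would be one-sided. The expected number in the no-regular arm is zero however long a patient stays, so all the loss falls in the regular arm. It would also grow as the plan came closer to its own 50% aim. Section 2.2 rests the precision statement on adherence and stresses its importance. Two analysts using different windows could therefore report different figures for the first primary outcome from the same patients, and could choose the window after seeing the data. The same question arises for death, non-fatal MI and permanent removal from the list.

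**Working it through.** **The plan's own figure.** Inputs from section 2.2: n = 144, true adherence 90%.

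1.96 × √(0.90 × 0.10 / 144) = 1.96 × 0.025 = 0.049

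This is ±4.9 points, so the stated ±5 reproduces. In patients it is 0.049 × 144 ≈ 7. It requires that all 144 can be scored.

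**The passages side by side.**

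1. Sections 1.1 and 7.0 compare tests done with tests expected. Section 2.1.1 says expected under what: the assigned strategy.
2. Section 5.1 ends that strategy at transplantation or another listed exit. The synopsis gives the same limit for transplantation. After exit, the strategy expects no test.
3. The two-test example concerns one kind of patient, who stays without symptoms through a 24-month treatment period. It is not a rule for patients whose treatment period ended sooner.
4. Section 6.0 stops following transplanted patients three months after surgery. A patient transplanted at month 15 is last seen at month 18, so a count to month 24 could not be completed from the planned data.

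These passages fit together only if the count stops at exit. On that count all 144 are scored and ±4.9 points stands. Dropping transplanted patients, which nothing in the plan suggests, would leave 72 and give 1.96 × √(0.09 / 72) = 0.069, or ±6.9 points.

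**Size if the literal 24-month count were used.** The documents do not give the schedule mix or the due dates, so these are assumptions. Let a be the share of the regular arm on the annual schedule, s the share transplanted, and q the chance that an annual-schedule patient is transplanted before the second test falls due. Patients on longer schedules are taken to contribute none.

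Patients scored differently = 72 × s × a × q

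- *No one overdue.* First test due uniformly over months 0–12, second 12 months later, transplant uniform over months 12–24: q = 0.5. With s = 0.5 this is 18a.
- *Two-thirds overdue, tested at month 1.* For them q = 1/12. Overall q = (2/3)(1/12) + (1/3)(0.5) = 0.222, giving 8a.
- *No one overdue, 15% transplanted.* 72 × 0.15 × 0.5 = 5.4, giving 5.4a.

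| Annual-schedule share a | None overdue (18a) | Two-thirds overdue (8a) | 15% transplanted (5.4a) |
|---|---|---|---|
| 28% | 5.0 | 2.2 | 1.5 |
| 50% | 9 | 4 | 2.7 |
| 100% | 18 | 8 | 5.4 |

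The 28% is the diabetes share in section 1.2.1. It is a low-end proxy, because Table 1 also puts most angiographic disease on the annual schedule. The 100% row is a bound only, since Table 1 has three frequencies.

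With 9 patients re-scored and every due test done, pooled adherence reads 1 − 9/144 = 93.75% and regular-arm adherence 1 − 9/72 = 87.5%, instead of 100%. The gap passes the planned half-width of about 7 patients when a exceeds 7.06/18 = 39% in the first model and 7.06/8 = 88% in the second. It never does so in the third, where the maximum is 5.4.

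**The case for a change.** The strongest case for a change is that truncation is nowhere written. Section 5.1 and the synopsis say when screening stops, not how adherence is counted, while the explicit counting rule in section 1.1 names two years. Section 7.0's window, read literally, even runs three months past transplantation. The gap touches about half the participants, the literal count errs in one arm only, and one sentence would remove the doubt.

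The omission, the arithmetic and the direction of the error all stand. Three stronger inferences do not:

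- *That the feasibility conclusion could turn on it.* Enrolment and consent have targets (24 per month and 40%). Adherence has none: 90% is the planning value for the interval, and the analysis is descriptive.
- *That 144 rests on adherence alone.* Section 4.0 also reaches it as 24 per month × 6 months, tied to the recruitment pace of the definitive trial.
- *That the 50% is unsound.* It is stated as an aim, section 3.1 concedes that transplant timing cannot be predicted definitively, and nothing in the documents shows it to be wrong.

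The obvious repair also has a trap. Counting only tests whose due date falls after randomisation would leave out the overdue test that section 3.1(c) schedules within a month of enrolment. A patient who took it would have one test more than expected and, under the equality rule in section 1.1, would be scored non-adherent.

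**Conclusion.** No change is needed. The plan leaves one step of a definition unwritten, but its parts point to one answer: expected tests are those that the assigned strategy calls for while the patient is on it, including an overdue test arranged at enrolment, up to the first exit in section 5.1 or 24 months. That reading keeps all 144 patients and the stated precision. The literal alternative expects wait-list screening from people who have left the list, and runs beyond their follow-up.

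If an analyst did use the literal count, about 2 to 9 of 144 patients would be re-scored with 50% transplanted and 28% to 50% on the annual schedule, depending on how many enter overdue. That is not trivial against a half-width of about 7 patients, but it would fall on a descriptive proportion with no threshold. Tests and transplant dates are already collected, so a report by arm of tests expected and done would show it.

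The sizes rest on assumed uniform timing and an assumed schedule mix. The conclusion rests on reading the sections together, and the study manual to which the protocol refers was not available.
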